### 6.2. Analysis of Pharmacodynamics (Biomarker) Endpoints

The pharmacodynamics endpoints are Hex4 and CK (as described in Section 2.3.3), which are considered biomarkers of muscle injury. These will be analyzed using descriptive statistics (n, mean, SD, 95% CI, median, Q1, Q3, minimum, and maximum) for the actual values, change and percent change from baseline, and presented by visit and by treatment group. Analysis will be conducted on the FAS population.

Line plots of mean  $\pm$  SE of the change (and percent change) from baseline over time will be provided for the PD endpoints (CK and Hex4).

### 6.3. Subgroup Analysis

The following analyses will be provided by visit and by prior ERT subgroups (as defined in Section 4.3.1) with the total.

- Summary of the main efficacy endpoints: 6MWD, % predicted FVC, MMT-lower extremities, PROMIS-Physical Function, PROMIS-Fatigue, and GSGC total score  
In addition, line plots of mean  $\pm$  SE of the change from baseline over time will be provided for the 6MWD and % predicted FVC only.
- Summary of PD endpoints: Hex4 and CK  
In addition, line plots of mean  $\pm$  SE of the change (and percent change) from baseline over time will be provided for the PD endpoints (CK and Hex4).
- Summary of exposure

- Summary of AEs: AE overview, TEAEs by SOC and PT, treatment-emergent serious adverse events (TESAEs) by SOC and PT, IAR overview, and IAR-TEAEs by SOC and PT
- Summary of demographics and baseline characteristics: demography (sex, age at informed consent)
- Summary of disposition: overall disposition table showing populations, number and percentage of subjects discontinuing the study, and reasons for discontinuation

Additional subgroup analyses based on the subsets of subjects defined in Section 4.3.2 will be conducted for the 6MWD and % predicted FVC, as described in Section 4.3.2.

## 7. ANALYSIS OF SAFETY

### 7.1. Safety Summary Statistics

Safety analyses will be performed on the OLE safety population. Safety data will be summarized using counts (number) and percentages for categorical data. Continuous data will be summarized using descriptive statistics (n, mean, SD, median, Q1, Q3, minimum, and maximum). No formal statistical tests will be performed.

### 7.2. Analysis of Adverse Events

Adverse events will be coded by system organ class (SOC) and preferred term (PT) using MedDRA version 23.0.

Summaries of AEs and SAEs will be focused on treatment-emergent adverse events (TEAEs) pertaining to Study ATB200-07 only. These are defined as any event that started or changed in the severity on or after the first dose of study drug in Study ATB200-07.

As stated in Section 5.2.3, AEs from ATB200-03 will be part of the medical history for ATB200-07. However, if those AEs worsened (or increased in severity) on/after first dose in ATB200-07, they will be considered as TEAEs for ATB200-07. For AEs occurring on Day 1 of ATB200-07, if the start time of the event is missing or if it occurred after the administration of the first dose of study drug, the event will be considered a TEAE.

In general, adverse events that occur more than 30 days from the last dose of study drug will not be counted as treatment-emergent. Therefore, if a subject permanently discontinues study drug and then gets an AE, the event will be considered as a TEAE only if it is within the TEAE tabulation period (in days) calculated as  $[(\text{last dose date of study drug} + 30 \text{ days}) - \text{first dose date} + 1]$  from the last dose date.

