## **13. ADVERSE EVENTS AND SERIOUS ADVERSE EVENTS**

### **13.1. Definitions**

#### **13.1.1. Adverse Events**

An AE is defined as any untoward medical occurrence in a patient or clinical investigation subject administered a pharmaceutical product, biologic (at any dose), or medical device, which does not necessarily have a causal relationship with the treatment. Therefore, an AE can be any unfavorable and unintended sign, symptom, or disease temporally associated with the use of a medical product, whether or not considered related to the medical product.

According to this protocol, expected or anticipated evolution of the disease under treatment will be evaluated as part of the disease symptom assessment. Changes in Pompe disease symptoms must be reviewed by the investigator or a medically qualified sub-investigator and recorded as “clinically significant” or “not clinically significant” in subjects’ source records (see [Appendix 3](#)). Expected or anticipated changes in the clinical condition may not qualify as AEs. However, if there is a clinically relevant worsening of a sign or symptom of the disease under treatment and the outcome fulfills the definition of an AE, it must be reported as directed in the protocol.

For subjects who participated in Study ATB200-03, any AE that begins after the first dose of open-label study drug will be considered a treatment-emergent adverse event (TEAE).

Subjects experiencing AEs should be followed up until their health has returned to baseline status or stabilized.

Adverse events include the following:

- the onset of new signs, symptoms, conditions, and illnesses
- exacerbation of pre-existing conditions or illnesses
- abnormal laboratory findings deemed clinically significant by the investigator
- physical examination changes deemed clinically significant by the investigator
- abnormal medical evaluation findings (eg, ECG) that are not documented at the last visit in Study ATB200-03 and/or, in the investigator’s opinion, represent a clinically significant change in the subject’s health during study participation

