## **13.2. Reporting of Adverse Events**

Information regarding AEs is to be obtained by questioning or examining the subject.

For subjects who participated in Study ATB200-03, AEs will be recorded in the eCRF and subject's source record beginning after the first dose of open-label study drug until 30 days after the last treatment visit.

A single diagnosis should be entered when known. If a clear diagnosis cannot be determined at the time of the eCRF and subject's source record entries, each sign and symptom must be recorded individually, until a final diagnosis is established. Pompe-related conditions, signs,

symptoms, etc, that are present in the subject's medical history should only be reported as AEs if they worsen (ie, increase in severity) during the subject's participation in the study.

For each AE reported, the date and time the event started and ended, action taken, outcome (resolved, resolved with sequelae, ongoing, or fatal), and severity must be noted.

All subjects who have AEs, whether or not considered associated with the use of study drug, must be monitored to determine the outcome. The clinical course of the AE will be followed up according to accepted standards of medical practice, even after the end of the period of observation, until a satisfactory explanation is found or the investigator considers it medically justifiable to terminate follow-up. Should the AE result in death, a full pathologist's report should be supplied, if possible. For all AEs that require or result in subject discontinuation from the study, relevant clinical assessments and laboratory tests will be repeated as clinically appropriate, until final resolution or stabilization of the event(s).

If the investigator considers it necessary to report a nonserious AE in a study subject more than 30 days after the last visit, he or she should contact Amicus to determine how the AE should be documented and reported.

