### **5.2.3. Medical History**

The AEs from Study ATB200-03 together with medical history collected for Study ATB200-07 will constitute the complete medical history for the OLE Study ATB200-07. Medical history will be coded using version 23.0 of the Medical Dictionary for Regulatory Activities (MedDRA) into system organ class (SOC) and preferred term (PT). The frequency of subjects with medical history will be summarized on the OLE safety population by SOC and PT and presented by treatment group and overall.

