### **7.2.1.2. Specific Summaries of TEAEs**

The number and percentage of subjects with TEAEs will be summarized in 2 ways as follows:

- by SOC and PTs, where the SOCs are ordered alphabetically and PTs within each SOC are sorted in order of decreasing frequency in the overall treatment group. A subject will be counted only once within the same SOC and within the same PT.
- by only PTs, where the PTs are sorted in order of decreasing frequency in the overall treatment group.

A summary of TEAEs by system organ class, preferred term, and severity will also be presented, where each TEAE will be counted under its maximum severity rating only.

The number and percentage of subjects with TEAEs leading to study drug discontinuation, TEAEs related to study drug (ie, treatment related TEAEs), TEAEs related to study drug and leading to study drug discontinuation, TESAEs, TESAEs leading to study drug discontinuation, TESAEs related to study drug (ie, treatment related TESAEs), TESAEs related to study drug and leading to study drug discontinuation, and death will be summarized by SOC and PT. All AEs will be provided in a listing that will include the subject identifier, SOC, PT, and the reported term, date of onset and study day, date of resolution and study day, the seriousness, the severity, the relationship to each individual study drug (for TEAEs), duration, the action taken, and the outcome. All TEAEs will be flagged in the listing. Additionally, subject data listings of deaths, SAEs, AEs leading to study drug discontinuation will be provided.

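### SAP 7.2 defines a TEAE by any change in severity, so read literally a pre-existing event that improves on study would count as treatment-emergent

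*SAP*

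**What the plan says.** SAP 7.2 limits the AE summaries to TEAEs of ATB200-07, which are "defined as any event that started or changed in the severity on or after the first dose of study drug" in that study. The next paragraph deals with AEs carried over from the parent study. They belong to the medical history, but "if those AEs worsened (or increased in severity) on/after first dose in ATB200-07, they will be considered as TEAEs for ATB200-07". SAP 5.2.3 sets the same default and shows that medical history has two sources: "The AEs from Study ATB200-03 together with medical history collected for Study ATB200-07 will constitute the complete medical history for the OLE Study ATB200-07".

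The protocol is directional throughout. Section 13.1.1 says that "any AE that begins after the first dose of open-label study drug will be considered a treatment-emergent adverse event (TEAE"), and its list of what counts as an AE includes "exacerbation of pre-existing conditions or illnesses". Section 13.2 says that Pompe-related conditions already in the medical history "should only be reported as AEs if they worsen (ie, increase in severity"). Section 12.3.7 sends any AE with a start date before the first open-label dose to medical history.

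For the severity table, SAP 7.2.1.2 says that "each TEAE will be counted under its maximum severity rating only". SAP section 1 gives the SAP precedence over the protocol on analyses and statistical methods.

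**The concern.** *Changed* covers a decrease as well as an increase. A programmer who implements the definitional sentence flags a pre-existing event that eases after Day 1. A programmer who implements the next paragraph leaves an eased ATB200-03 event in medical history. One section thus supports two derivations of the same flag.

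Safety is the primary objective, and the TEAE flag feeds the AE overview, the tables by system organ class and preferred term, the severity and relatedness tables, the IAR-TEAE tables, and the AE summaries by prior ERT status. Recovery counted as a new event would inflate those counts. This would be most awkward in the switched group, where an event that arose on alglucosidase alfa/placebo and then eased could be attributed to the period on cipaglucosidase alfa/miglustat.

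**Working it through.** The documents attach no figure to this point, so the check compares texts.

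**Which events the severity limb affects.** An event that starts on or after the first ATB200-07 dose already qualifies through *started*. The severity limb therefore matters only for events present before that dose. Three cases cover them:

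| Pre-existing event, after the first ATB200-07 dose | SAP 7.2, general definition | SAP 7.2, next paragraph (ATB200-03 AEs only) | Protocol 13.1.1 |
|---|---|---|---|
| Worsens | TEAE | TEAE | An AE, as an exacerbation |
| Unchanged | Not a TEAE | Not a TEAE | Not a new AE |
| Improves | **TEAE** | Not a TEAE; stays medical history | Neither a TEAE nor a new AE |

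The texts part company on the direction of change only in the third row, where the general definition stands alone.

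**Whether another text settles the third row.**

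- The next paragraph of SAP 7.2 says *if*, not *only if*. With medical history as the default and worsening as the exception, its intent is still plain. It names only ATB200-03 AEs. For conditions entering through the other source in SAP 5.2.3, the undirected definition is the only SAP rule.
- The protocol points the right way but does not override the SAP, because SAP section 1 gives the SAP precedence. Protocol 13.2 is also narrower than it may look, since its worsening rule covers Pompe-related conditions only.

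**How an improving event could reach the tables.** It would first have to exist as an ATB200-07 AE record. Protocol 12.3.7 starts AE reporting after the first open-label dose and puts earlier events into medical history. Protocol 13.1.1 lists exacerbation, not improvement, as a reason to record an AE. Few improving events should therefore reach the AE data. The documents give no count of events ongoing at the first dose and no rate of improvement.

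**Which outputs are exposed.** These are the TEAE tables in SAP 7.2.1, the IAR-TEAE tables in SAP 7.2.2, and the AE summaries by prior ERT status in SAP 6.3. Exposure (SAP 5.3), laboratory data (7.3), and vital signs and ECG (7.4) have their own criteria and do not use the AE flag.

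**The case against.** The strongest reply is that the SAP already governs the obvious example. An ATB200-03 event that eases is medical history by default and becomes a TEAE only through the worsening exception. The specific rule follows the general sentence and supplies its direction. Data capture adds a second barrier, because events that start before the first dose should not be in the AE data unless they worsen. The analyses are descriptive, with no formal tests, and any residual error would overstate harm, not hide it.

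Most of this stands, and it is why the point is minor. It does not remove the conflict. The general sentence still says something different from the paragraph after it, and that paragraph does not reach pre-existing conditions other than ATB200-03 AEs.

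A reader might also infer that a recovering event would appear as a severe TEAE, because the maximum-severity rule is not limited to ratings after the first dose. That needs three steps: the improving event is entered as an ATB200-07 AE, it is flagged despite the next paragraph, and its pre-dose grade is held in that record. Protocol 13.2 asks for a severity for each AE but describes no tracking of grades across the two studies, so the documents do not show that this would happen.

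**Conclusion.** The definition is wrong as written, and the severity is minor. Applied literally, SAP 7.2 classifies an improving pre-existing event as treatment-emergent, against its own next paragraph and the protocol's wording.

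Two stronger readings are not supported:

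- A reader might infer that every safety table is affected. Only the tables that use the AE or IAR TEAE flag are.
- A reader might want to put a number on the false TEAEs. That needs the number of events ongoing at the first dose, the share that ease, and the share of those that reach the AE records. The documents give none of these, so any estimate would rest wholly on invented inputs.

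The judgement that the effect is probably small assumes that sites follow Protocol 12.3.7 and that programmers read the two paragraphs of SAP 7.2 together.

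**What to change.** In SAP 7.2, reword the definition so that a TEAE is an event that *started, or worsened (increased in severity) relative to its severity before the first ATB200-07 dose*, on or after that dose. One rule then covers all pre-existing events, whether from ATB200-03 or from other medical history. It agrees with the next paragraph of SAP 7.2 and with the exacerbation wording in Protocol 13.1.1.

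Optionally, add to SAP 7.2.1.2 that for a worsened pre-existing event the tabulated severity is the maximum on or after the first ATB200-07 dose.

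The cost is one sentence in the SAP and one condition in the flag derivation, plus a second sentence if the optional addition is taken. No new data are needed.

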For all subjects, AEs and SAEs will be reported from time of first dose of open-label study drug until 30 days after the last dose of study drug. If the investigator becomes aware of an SAE in a subject or receives an unsolicited report of an SAE from a subject more than 30 days after the last treatment, and considers the event possibly, probably, or definitely related to previous study treatment, he or she should contact the Amicus medical monitor to determine how the SAE should be documented and reported.

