## 4.4. Data Handling

### 4.4.1. Study Day

For the purposes of analysis, the date of first dose of study drug (First Dose Date) in ATB200-07 is designated as Day 1 and it will serve as the reference start date. The following relative days are considered:

- Total duration of treatment (ie, exposure) will be calculated as: (last dose date prior to data cutoff – first dose date) + 1.
- If the date of interest occurs on or after the first dose date, then study day will be calculated as: (date of interest – first dose date) + 1.
- If the date of interest occurs prior to the first dose date, then study day will be calculated as: (date of interest – first dose date).

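### The SAP counts its TEAE period from the last dose instead of the first, so the formula contradicts the 30-day limit it is meant to apply

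*SAP*

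**What the plan says.** SAP 7.2 defines a TEAE as an event that starts or changes in severity on or after the first dose in Study ATB200-07. It then closes the period twice.

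- In words: "adverse events that occur more than 30 days from the last dose of study drug will not be counted as treatment-emergent", introduced as a general rule.
- As a calculation, offered as a consequence of that rule for an AE arising after permanent discontinuation: "the event will be considered as a TEAE only if it is within the TEAE tabulation period (in days) calculated as". The expression given there adds 30 days to the date of the last dose, subtracts the date of the first dose and adds 1. The sentence ends by counting these days from the last dose date.

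SAP 4.4.1 makes the first ATB200-07 dose Day 1. "If the date of interest occurs on or after the first dose date, then study day will be calculated as" the date of interest minus the first dose date, plus 1. The TEAE bracket has the same form.

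The protocol does not settle the matter. Its TEAE definition (Protocol 13.1.1) gives a start and no end. Protocol 13.1.2 says "AEs and SAEs will be reported from time of first dose of open-label study drug until 30 days after the last dose", and Protocol 13.2 has AEs recorded "beginning after the first dose of open-label study drug until 30 days after the last treatment visit". Both govern what is collected, not how a record is flagged. SAP Section 1 states that the SAP's methods supersede the protocol's.

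**The concern.** The second sentence is offered as a consequence of the first, yet the two give different answers. The bracket measures the whole span from first dose to 30 days after the last dose. Starting that span at the last dose adds the subject's entire treatment duration to the intended 30 days.

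The TEAE flag feeds the AE overview, the SOC/PT tables, the severity, relatedness and seriousness summaries, the IAR tables and the listing flags. Safety is the primary objective and the stated focus of the final CSR. Two programmers working from adjacent sentences could flag the same late record differently, and the formula is the sentence more likely to be coded.

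**Working it through.** **Inputs**

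- Limit in words: 30 days after the last dose (SAP 7.2).
- Period: P = (last dose date + 30) − first dose date + 1, counted from the last dose date (SAP 7.2).
- Exposure: D = last dose date − first dose date + 1 (SAP 4.4.1). D is also the study day of the last dose.
- Planned maximum sample size: about 110 (SAP 3.3).

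**Step 1. Length of the period.** P = (last − first + 1) + 30 = D + 30.

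**Step 2. Counted from first dose as Day 1.** The period closes on study day D + 30. The last dose is on study day D, so the time off drug is (D + 30) − D = 30 days. This reproduces the SAP's 30-day limit for any D.

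**Step 3. Counted from the last dose, as written.** The period closes on study day D + (D + 30) = 2D + 30. The time off drug is D + 30 days, which exceeds the limit by D days. For D = 91 it closes on study day 212, and for D = 365 on study day 760.

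| D (days) | P | Days off drug, counted from first dose | Days off drug, counted from last dose | Excess over 30 |
|---|---|---|---|---|
| 1 | 31 | 30 | 31 | 1 |
| 15 | 45 | 30 | 45 | 15 |
| 85 | 115 | 30 | 115 | 85 |
| 91 | 121 | 30 | 121 | 91 |
| 365 | 395 | 30 | 395 | 365 |
| 729 | 759 | 30 | 759 | 729 |
| 1639 | 1669 | 30 | 1669 | 1639 |

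The durations are illustrative. Days 15, 85, 365, 729 and 1639 are the SAP Table 2 target days for Weeks 2, 12, 52, 104 and 234.

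If the last dose date itself is counted as day 1, the limit is D + 29 and the excess is D − 1. Only a subject with a single dose then gets exactly 30 days.

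**Step 4. Effect on a table.** One misflagged subject changes an overall percentage by 1/110 = 0.9 percentage points. In the SOC/PT tables (SAP 7.2.1.2), "A subject will be counted only once within the same SOC and within the same PT", so the row changes only if that subject has no other event in it. The same holds for an overview row if that row counts subjects. The shift is larger within either treatment group, because the denominator is smaller; the documents do not give the group sizes.

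**The case against.** The best case for leaving the text alone is that nobody would be misled. The 30-day rule stands in plain words one sentence earlier, the formula is presented as following from it, and the bracket names first dose and last dose + 30 as its own endpoints. On that view this is a wording slip.

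Its effect may also be nil. Routine collection ends about 30 days after the last dose or last treatment visit. Protocol 12.2.6 describes the follow-up visit as monitoring AEs already ongoing. Later events come in only when the investigator contacts the sponsor about how to document them (Protocol 13.1.2, 13.2 and 13.3), so entry in the database is not assured. Subjects still on drug at the 31 December 2024 cutoff have not discontinued, and the cutoff also shortens the literal window for those who stopped late. No tests are planned, and every AE is listed with its onset study day, so a misflag could be found.

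Most of this stands, and it limits the consequence. It does not remove the contradiction, because nothing elsewhere in either document corrects the formula. Late records are also possible. Protocol Table 4 places follow-up at 30 days or more after the last dose and collects AEs there. Related SAEs learned of later go to the medical monitor, and these are the events that would enter the sparse related-TESAE rows.

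A rewritten rule could also change more than the anchor: SAP 7.2 speaks of a change in severity, its 30-day rule is qualified as general, and SAP 4.7.1 treats certain AEs with a missing start date as treatment-emergent. That is a fair caution for the redrafting, and changing only the anchor avoids it.

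**Conclusion.** The formula is wrong as written. It has the right length for a period starting at first dose but is counted from the last dose, so it permits D + 30 days off drug where the SAP intends 30. The excess equals the time on treatment: 91 days after 91 days on drug, and 365 after 365.

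These are window lengths, not event counts. The documents do not say how many AEs were recorded with onset more than 30 days after the last dose, and the number is probably small. Only subjects who permanently discontinued and have such a record can be affected. The figure of about 0.9 points per misflagged subject assumes a denominator of 110 and no other event for that subject in the row.

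Confidence in the contradiction is high. A material change to the safety tables is not shown. The correction should still be made, because this rule determines the flag used throughout the primary-objective tables.

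**What to change.** Change the anchor in the last sentence of the TEAE definition in SAP 7.2, in either of two ways:

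- keep the formula and count the period from the first ATB200-07 dose as Day 1, as in SAP 4.4.1; or
- drop the formula and state that an AE is treatment-emergent if its onset or worsening falls on or after the first ATB200-07 dose and on or before the last dose date + 30 days.

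Both give the same end date. The first touches nothing else. If the second is used, the Day 1 start-time rule in SAP 7.2 and the missing-start-date rule in SAP 4.7.1 should be stated to remain in force.

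The cost is one sentence in the SAP, with no new data and no burden on subjects. If programming has begun, the TEAE derivation should be checked against the corrected sentence.
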